#### TEST SITES

This study will be performed in two different times at two different sites. Two sites will be chosen based upon the absence of mosquito-borne disease and adequate mosquito populations. The first site will be at the following address:

The Savannah-Ogeechee Canal Museum & Nature Center [name] Savannah, Georgia 31419

The second site will be at the following address:

Pine Island, Florida Lee County Mosquito Abatement District

#### TEST ORGANISM(S)

Natural adult populations of mosquitoes found in the Coastal area of Georgia will be the test organisms. The anticipated species occurring in this test area should be primarily *Aedes vexans*, *Psorophora ferox* and *Ochlerotatus infirmatus* plus other minor occurrences of native species.

Natural adult populations of mosquitoes found in the Gulf Coast area of Florida will be the test organisms. The predominant species in this test area is anticipated to be *Ochlerotatus taeniorhynchus* plus other minor occurrences of native species.

Specimens will be collected from landings on the ICR staff at both sites and returned to the laboratory for identification by a Board Certified Entomologist.

#### **SUBJECTS**

Human subjects are required for this study because they represent the feeding target of the mosquitoes. The purpose of these repellents is to prevent mosquitoes from biting humans. There are no satisfactory substitute models for testing repellency to mosquitoes. While there has been experimental work on product repellency accomplished using mice or guinea pigs, the data did not give reliable results when compared to data gathered from human subjects.

ICR, Inc., (ICR) policy complies with the Department of Health and Human Services Policy at 45 C.F.R. pt. 46 and 45 C.F.R. §§ 46.109, 46.116, and the EPA Part 26 model rule at 40 C.F.R. pt. 26 Subparts K and L, when human volunteers are used. Thus ICR submits a protocol, informed consent

Page 9 of 31

<sup>1 Busvine, James R. 1971, A Critical Review of the Techniques for Techniques for Testing Insecticides, Commonwealth Agricultural Bureaux, England, p 233-245

Protocol No.: G0590307001A044 ICR Project No.: 0307-059-0155

document, and standard indemnification forms to an independent institutional review board (IRB) set up to ensure that the rights and welfare of the participants are protected and that the study is carried out in an ethical manner.

ICR uses the following IRB for this service:

Essex Institutional Review Board, Inc. [name] [name]

This IRB is accredited by PHRP, and is in the process of obtaining accreditation from AAHRPP.

Approval of all documentation for human volunteer testing must be obtained before such testing can occur.

ICR has developed a pool of male and female test subjects. The test subjects we recruit represent a diverse group including professionals such as working teachers, business owners and engineers, as well as students, housewives and others. They are available to travel for field tests. ICR will recruit 14 subjects from this group for each location (a total of 28).

ICR will exclude pregnant and breastfeeding women from this study due to ethical concerns. We will also exclude children under the age of 18 for the same reason. Non-English speaking individuals will be excluded to ensure that comprehension and understanding of the ICD and test parameters is without question. Full time employees of either ICR, Inc. or the sponsor will be excluded to ensure that coercion is not an issue. Individuals sensitive to either mosquito bites, insect repellents, or skin care skin products will be excluded to avoid placing them at risk. Although the groups of people that ICR would exclude from using as test subjects would certainly represent individuals that could use repellents, we feel justified for not including them for the reasons that are mentioned above.

ICR will only include individuals attesting to be healthy in this study who are available to travel to distant field locations. These subjects need to be capable of reading and understanding English.

The database of potential test subjects that we select our subjects from, is as representative of potential repellent users as we are able make it in terms of both practical and ethical considerations. Our test subjects need to be in good health to withstand the rigors of field testing. They must be available to travel to out of state test locations. Test subjects must be able to speak and understand English in order to truly be informed and comprehend the scope of the study as explained to them. We will accept individuals between the ages of 18 to 65. This age group represents a large portion of the population who through their diverse activities would both encounter mosquitoes and could have a need to use insect repellents.

Page 10 of 31

Protocol No.: G0590307001A044 ICR Project No.: 0307-059-0155

ICR will select individuals from our database of potential test subjects. This will be accomplished by drawing numbers that correspond to a particular test subject. We will attempt to select even numbers of male and female test subject to eliminate any gender bias to attractiveness to mosquitoes.

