#### **NEGATIVE CONTROL**

Sufficient biting pressure (i.e., mosquito landing rates in the range of 1 to 10 per minute in a 250 cm^2 area on each of the exposed untreated control arms for up to a 5 minute period) will be confirmed at the commencement of the study and throughout the study. One untreated arm of each of the two control subjects will serve as negative controls. These controls will be selected at random from the total pool of test subjects by drawing names. Different subjects will be used as controls for each day of the study. This will be accomplished by removing the names of subjects already used as negative controls from the pool when drawing names of subjects to be used for the next day's test.

Negative controls will be used to monitor the level of mosquito activity in the area by baring the 250cm² untreated area on their arm for up to five minutes every one-half hour while the study director or an assistant counts the number of mosquitoes which land on the bare skin. If the stated landing rate has been verified prior to the end of the five minute period, the control will stop exposing their bare arm to mosquitoes. To minimize the number of bites, the mosquitoes will be brushed away with the tip of a pencil or pen after being counted. The negative controls are also protected by covering the untreated test area with the shirt sleeve in between the 5-minute test sessions. Like the treated test subjects, the negative controls will be protected with a head net and latex or vinyl gloves.

The negative controls will not be exposed to any repellent related risk.

Page 11 of 31

Protocol No.: G0590307001A044 ICR Project No.: 0307-059-0155

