#### Treatment Groups

There will be two groups for each test location(Georgia and Florida): a treated group of twelve subjects whose arms will be treated, and an untreated (control) group of two test subjects whose arms will be untreated. Subjects will be given a subject number. They will be assigned to the groups by lottery selection of the subject number.

Page 19 of 31

Protocol No.: G0590307001A044 ICR Project No.: 0307-059-0155

Personnel preparation

All test subjects will complete and will sign an "Informed Consent Document" prior to acceptance as a test participant.

On the evening prior to the first day of testing, the outside of the shoes of each test subject, the controls and the ICR staff will be treated with a 0.5% permethrin aerosol to help prevent ticks from crawling on test participants in the test areas. This treatment will not affect the test but will help protect the people involved from ticks. Permethrin has a low vapor pressure and will not interfere with the repellency of the treated arms.

Females will be required to perform an over the counter pregnancy test that will be supplied by ICR. They will do this the morning of the test. The results will be verified by a qualified female ICR staff member. They may not participate if they are pregnant or breastfeeding. The results of this pregnancy test will be kept confidential and will not be disclosed to anyone other than the test subject and the P.I..

The evening before the study is scheduled to begin, the test subject's arms will be measured in the following manner for demarcation of the 250 cm^2 test area:

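### The control lottery takes no account of sex, so even from 7 men and 7 women both controls are the same sex in 46% of draws, which partly undoes the protocol's own aim of sex balance

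*Protocol*

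**What the plan says.** The Subjects section describes how people are taken from the laboratory's database: "This will be accomplished by drawing numbers that correspond to a particular test subject". The next sentence gives the aim: "We will attempt to select even numbers of male and female test subject to eliminate any gender bias to attractiveness to mosquitoes". Each location receives 14 subjects, 28 in all.

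Treatment Groups splits the 14 into "a treated group of twelve subjects whose arms will be treated, and an untreated (control) group of two test subjects whose arms will be untreated". On how the split is made, it says: "They will be assigned to the groups by lottery selection of the subject number". Study Overview also says that treated and control subjects are chosen by lottery on the study day. Negative Control describes the same step for the controls: "These controls will be selected at random from the total pool of test subjects by drawing names". It adds "Different subjects will be used as controls for each day of the study", which is achieved by taking earlier controls out of the pool before the next draw. None of these three sections mentions sex.

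The controls have one task: "Negative controls will be used to monitor the level of mosquito activity in the area". Their landing counts, taken about every half hour, must reach 1 to 10 per minute on each control arm.

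**The concern.** The protocol itself treats sex as a possible source of bias in attractiveness to mosquitoes and wants the numbers even for that reason. The step that follows selection can undo whatever evenness selection achieves, because it draws two people out of 14 without regard to sex.

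Two things depend on that draw. The first is the pressure check. Two people per location show whether enough mosquitoes are biting, and their counts feed decisions: low density may move the group to an alternate site (Study Overview), and insufficient insect activity is a ground for cancelling (Criteria for Test Cancellation). If the sexes differ in attractiveness, two controls of one sex are a poorer gauge of the pressure on a mixed treated group. The second is the make-up of the treated group. Each product's mean protection time comes from ten to twelve people per location, and their sex mix is left partly to chance.

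**Working it through.** **Inputs**
- Subjects per location: 14, and 28 in total (Subjects).
- Split: 12 treated and 2 controls (Treatment Groups).
- Draw of controls: simple random, from the whole pool (Negative Control; Treatment Groups; Study Overview).
- Starting sex mix: not given. The case most favourable to the protocol is that its aim is met exactly, at 7 men and 7 women. Less even mixes are shown for range.

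**The plan's own figure.** Number of subjects and Rationale for Sample Size gives 10 treated + 2 additional treated + 2 controls = 14 per location. Two locations give 28. This agrees with the Subjects section.

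**Control draw.** With m men among 14, the chance that both controls are of one sex is

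[C(m,2) + C(14−m,2)] / C(14,2), where C(14,2) = 91.

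| Men : women selected | Same-sex pairs | Probability |
|---|---|---|
| 7 : 7 | 21 + 21 = 42 | 42/91 = 46.2% |
| 8 : 6 (or 6 : 8) | 28 + 15 = 43 | 43/91 = 47.3% |
| 9 : 5 (or 5 : 9) | 36 + 10 = 46 | 46/91 = 50.5% |
| 10 : 4 (or 4 : 10) | 45 + 6 = 51 | 51/91 = 56.0% |

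From 7:7, the other 7 × 7 = 49 pairs have one control of each sex: 49/91 = 53.8%, with the treated group at 6:6. In the 46.2% of same-sex draws, the treated group is 7:5.

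**Both locations.** With 7:7 at each and one control draw at each, the chance of same-sex controls at one or both locations is 1 − (49/91)² = 71.0%.

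**A second test day at the same location.** Earlier controls leave the control pool, so the second pair comes from 12 people.
- After a mixed first pair, 6:6 remain: 2 × C(6,2)/C(12,2) = 30/66.
- After a same-sex first pair, 5:7 remain: [C(5,2) + C(7,2)]/C(12,2) = 31/66.
- Overall: (49/91)(30/66) + (42/91)(31/66) = 46.2%.

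Removing earlier controls therefore does not change the chance on a later day.

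**After the change.** With one man and one woman drawn by lot, the chance of same-sex controls is 0. From 7:7, the treated group is always 6:6 at assignment.

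**The case against.** The strongest objection is that little follows from the imbalance.
- Experimental Design puts one product on each arm of every treated subject, so sex cannot confound A against B. This stands.
- Data Analysis plans means, standard deviations and confidence limits of protection time. It plans no treated-versus-control contrast and no contrast between Georgia and Florida. This also stands, so a site comparison blurred by sex mix is not part of the point.
- The pressure check is a threshold with a tenfold band, 1 to 10 landings per minute. Staff also measure landing rates when choosing locations, and all subjects must be attractive to mosquitoes. No size of sex effect is given, so nobody can show that same-sex controls would change a pass or fail. This stands too, and it limits the point to representativeness.
- The even-numbers aim is attached to selection from the database, not to the control draw, so the protocol does not contradict itself. That is right. The lottery works against the purpose of the aim without breaching a stated rule.

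A reader might go further and infer that the protocol promises balance and that the database draw also ignores sex, so that balance is usually lost. If that draw were sex-blind and the database large and half male, exactly 7:7 would arise in only C(14,7)/2¹⁴ = 21% of draws. The document does not support this reading. It speaks of an attempt, and the even-numbers sentence follows directly on the drawing of numbers and plausibly constrains it. It also gives neither the size nor the sex mix of the database. That the section does not spell out how even numbers are reached is a missing detail, not evidence that sex is ignored.

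**Conclusion.** The point holds for the control lottery only. Starting from an exact 7:7 selection at a location, both controls are the same sex in 46.2% of draws. The treated group is then 7:5 instead of 6:6, and the check on biting pressure comes from one sex. The figure assumes a simple random draw of two from 14, as the protocol describes, and it rises slowly as the starting mix becomes less even.

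Balance is not usually lost on this basis: from 7:7 it is kept in 53.8% of draws, and when lost it goes only to 7:5. Whether the imbalance matters in practice depends on a sex difference in attractiveness that the protocol contemplates but does not quantify. The comparison of the two products is unaffected. This is a minor matter, worth changing because the change is free.

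**What to change.** In Study Overview, Negative Control and Treatment Groups, state that on each test day one control is drawn by lot from the men and one from the women. Keep the existing rule that earlier controls are removed from the pool before the next day's draw.

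Starting from 7:7, the treated group is then 6:6 at assignment. That balance is not guaranteed to last: Number of subjects and Rationale for Sample Size foresees dropouts and exclusion for a positive pregnancy test, and the latter can remove only women. Because the landing criterion applies to each control arm, it would then have to be met on one man and one woman. The hourly whole-body count uses a single control and is not improved by this change.

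The cost is one sentence in each of three sections. Selection stays random, and no subjects, procedures or exposures are added.

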#### REMUNERATION

All travel costs, as well as lodging and food expense, for the subjects will be paid by ICR. The subjects will be paid \$11/hour for a typical 9-hour travel day, for a total payment of \$99 for the day. For working days that go beyond 9 hours, the subjects will be paid at a rate of time and one half (\$16.50/hour) for the overtime hours. The payment for a 12 hour test day will be \$ 148.50 for 12 hours plus \$16.50 for any additional hours beyond 12. Payment will be mailed to the subject at the conclusion of the field portion of the study.

All subjects will have signed "Informed Consent Statements" prior to acceptance as a study participant. The Informed Consent Document will be formally explained to all of the test subjects before the study is scheduled to begin. If any test subject refuses to sign after learning the details of the document, they will not be allowed to participate in the study. To try to avoid this inconvenience, the informed consent will be explained to each test subject, either in person, on the telephone, and by mailing ICDs prior to the study, to try to eliminate any potential test subject not interested in the project. The "Informed Consent Document" will have been approved by an Institutional Review Board before it is presented to the test subjects.

#### **NEGATIVE CONTROL**

Sufficient biting pressure (i.e., mosquito landing rates in the range of 1 to 10 per minute in a 250 cm^2 area on each of the exposed untreated control arms for up to a 5 minute period) will be confirmed at the commencement of the study and throughout the study. One untreated arm of each of the two control subjects will serve as negative controls. These controls will be selected at random from the total pool of test subjects by drawing names. Different subjects will be used as controls for each day of the study. This will be accomplished by removing the names of subjects already used as negative controls from the pool when drawing names of subjects to be used for the next day's test.

Negative controls will be used to monitor the level of mosquito activity in the area by baring the 250cm² untreated area on their arm for up to five minutes every one-half hour while the study director or an assistant counts the number of mosquitoes which land on the bare skin. If the stated landing rate has been verified prior to the end of the five minute period, the control will stop exposing their bare arm to mosquitoes. To minimize the number of bites, the mosquitoes will be brushed away with the tip of a pencil or pen after being counted. The negative controls are also protected by covering the untreated test area with the shirt sleeve in between the 5-minute test sessions. Like the treated test subjects, the negative controls will be protected with a head net and latex or vinyl gloves.

The negative controls will not be exposed to any repellent related risk.

Page 11 of 31

Protocol No.: G0590307001A044 ICR Project No.: 0307-059-0155

#### POSITIVE CONTROLS

A positive control is intentionally excluded from the proposed study protocol for several reasons. The sponsor understands that such practice is generally discouraged in these types of studies by the EPA/OPP and that positive controls in these types of studies are optional. Data on a positive control group serves no purpose in this study to confirm the mosquito repellency of the test product and determine a reliable protection period under real-life field conditions. Putting additional subjects at risk, however minimal, to include a positive control group is not necessary.

#### SUPPORT STAFF

Additional ICR staff members will support the Study Director and test subjects in their activities. ICR staff members, along with the Study Director, will record all test data. Test subjects will not record any data. The study results would be difficult to defend in an EPA audit or in a court of law if a test subject records data.

ICR staff have been hired on the understanding that field study participation is a condition of employment. All details of field testing are outlined to potential employees prior to their accepting a position at ICR, Inc.

To meet one of the GLP requirements, a QA representative will monitor the study conduct and prepare phase inspection reports.

#### **MISCELLANEOUS**

Stools, syringes, latex and vinyl gloves, aspirators and vials, clip boards, head nets, duct tape, data record forms, scissors, elastic bandages, or Velcro® straps, Elastikon® tape, pencils, marking pens (e.g. Sharpie®), sling psychrometer, anemometer, unscented Neutrogena® soap, paper towels, ice chest and ice, camera, mechanical counters.

#### RECORDS TO BE MAINTAINED

All study notes, data collection sheets (true copies), SOPs (originals), Chain of Custody letters (true copies), Sample Log and Sample Record of Use Forms (true copies), the protocol (true copy) and signed Informed Consent documents will be maintained in the ICR archives. The original documents will be provided to the sponsor for archiving with the exception of SOPs, Master Schedules, signed Informed Consent documents, test sample characterization, and personnel files.

Page 12 of 31

CR

Mosquito Repellent Field Test, Florida & Georgia

Protocol No.: G0590307001A044 ICR Project No.: 0307-059-0155

#### RISK CHARACTERIZATION AND MINIMIZATION

The subjects will be exposed to three types of risk:

1. They will be treated with a test repellent.

The active ingredient, Picaridin® demonstrates a low acute oral, dermal and inhalation toxicity. It is classed as Category IV for acute inhalation toxicity and primary dermal irritation. It is not a dermal sensitizer. The EPA "New Pesticide Fact Sheet" indicates that the toxicology data base for the active ingredient is complete and no additional studies are required.

There is minimal risk for subjects to experience an adverse reaction to the insect repellents being tested. The study sponsor that developed the test repellents has over 120 years of experience formulating and producing a wide variety of cosmetics and personal care products with worldwide sales.

All of the inert ingredients used in the finished insect repellent products have a long history of safe use in various personal care and cosmetics products.

Moreover, the sponsor has confirmed that all of the inert ingredients used in each of the test repellents have been previously reviewed and approved by EPA for use in FIFRA registered insect repellent products.

While there is low concern for the toxicity potential for the test samples to induce an adverse reaction in the test subjects, they will be monitored throughout the study and prompt medical attention will be obtained if any adverse reaction is observed among the subjects on test. Those individuals who are known or claim to have allergies to mosquito bites, insect repellents, or skin care products will be excluded from participation in the study.

2. They will be exposed to bites from mosquitoes.

All subjects known to have severe reactions to mosquito bites will be excluded from this study.

All subjects will be issued head nets and a choice of latex or vinyl gloves. Only a small area (250 cm²) of skin on each arm will be exposed. All other parts of the body will be covered with the subject's personal clothing. The exposed areas will be covered immediately upon receiving a FCB on that area. Caladryl® or Calamine® lotion and rubbing alcohol will be available at the study site for use to mitigate any reaction to mosquito bites.

3. They may be exposed to vectors of arthropod-borne diseases

Page 13 of 31

Mosquito Repellent Field Test, Florida & Georgia

Protocol No.: G0590307001A044 ICR Project No.: 0307-059-0155

It is recognized that mosquitoes are vectors of many diseases and this issue is clearly communicated to potential test subjects. Since the EPA requires demonstration of the repellency of mosquitoes known to carry specific diseases such as the WNV in order to substantiate related product claims, the sponsor is compelled to conduct field testing in areas in which test subjects will attract these potential vector species. While the potential for contracting disease cannot be fully eliminated, that risk is reduced by avoiding conduct of the study in an area known to be associated with current incidents of mosquito and other insect-borne disease. Appropriate mosquito abatement authorities in the region of the proposed test site will be consulted immediately prior to the initiation of the field study to confirm that there has been no recent outbreak of mosquito or other insect-borne disease in that area.

The CDC estimates that only about 1 in 5 people who contract WNV will be affected. About one in 150 people infected with WNV will develop severe illness and about 4 of 5 will show no symptoms. Most people who have developed serious symptoms have been the elderly or those with a compromised immune system. The principal carriers of the WNV belong to the Culex genus (a genus is a group of similar species). This particular genus of mosquitoes is not common in areas where we will be conducting the study. While the risk of contracting WNV is considered to be low, no guarantees can be offered.

Georgia reported 8 cases of West Nile Virus, one case of Eastern Equine Encephalitis, one case of La Crosse Encephalitis in 2006. The La Crosse Encephalitis affects predominantly children under the age of 16.

Of the 8 cases reported in Georgia, one incidence of the West Nile Virus was reported for Chatham County, the proposed Georgia site of the study.

Florida reported 3 cases of West Nile Virus, one case of Eastern Equine Encephalitis and no other arbovirus type cases in 2006. None of these cases occurred in Lee County, Florida, the proposed study site.

Both the Mosquito Abatement Districts in Chatham County, Georgia, and in Lee County, Florida, monitor for disease bearing mosquitoes on a weekly basis and have agreed to supply ICR with that data for one week before and one week during the test. The study will be conducted only if surveys prior to the test are negative.

To minimize the threat from ticks, on the evening prior to the day of testing, the outside of the shoes to be worn during testing, of each subject and the ICR staff will be treated with a 0.5% permethrin aerosol to stop any ticks in the test areas from crawling onto the test subjects. No one will be wearing the shoes when the shoes are treated so that the spray will not hit any skin that will be treated in the test, or clothing that will be near the treatment area. The spray will be dry before the test begins and it will not be reapplied during the course of the test.

Page 14 of 31

Mosquito Repellent Field Test, Florida & Georgia

Protocol No.: G0590307001A044 ICR Project No.: 0307-059-0155

The subjects will only need to receive two mosquito bites in each of the 250 cm^2 treatment areas within 30 minutes to confirm breakdown, after which the exposed area is covered. Additionally, risk is minimized due to limiting study subject exposure to 5 minute intervals every 30 minutes. All of the above factors combined will minimize disease and bite risk. Thus the risk to the test subjects is no more than one which they would experience in normal outdoor activities.

There will be First Aid qualified staff members on site, and First Aid supplies will be available at the test site at all times. A selected local hospital will receive prior notification of this study and on-site staff will have cell phones to make emergency calls if necessary. In the case of medical emergency people will be transported to the selected local hospital by either ICR staff or professional ambulance.

The Savannah-Ogeechee Canal Museum & Nature Center, Savannah, GA study site the following hospital will be available:

Distance from the study site - 10 miles
St. Joseph Candler Health System
[name]
Savannah, GA. 31405 [contact]

For the Pine Island, Lee County, Florida study site the following hospital will be available:

Distance from the study site - 25 miles Cape Coral Hospital [name] Cape Coral, Florida 33904 [contact]

If any test subjects need medical attention, their medical care will be paid by ICR.

